3.3.4 Withdrawal of patients from therapy or assessments

Patients may potentially be withdrawn from trial treatment or from the trial as a whole (“withdrawal of consent”) with very different implications, please see [Sections 3.3.4.1](#) and [3.3.4.2](#) below.

Every effort should be made to keep the patients in the trial: if possible on treatment, or at least to collect important trial data.

Measures to control the withdrawal rate include careful patient selection, appropriate explanation of the trial requirements and procedures prior to enrolment, as well as the explanation of the consequences of withdrawal.

The decision to withdraw from trial treatment or from the whole trial as well as the reason must be documented in the patient files and electronic case report form (eCRF).

3.3.4.1 Withdrawal from trial treatment

An individual patient is to be withdrawn from trial treatment if:

- The patient wants to withdraw from trial treatment, without the need to justify the decision.
- Has radiological (or clinical) documentation of progressive disease on the current treatment.
- The patient needs to take concomitant drugs that interfere with the investigational product or other trial medication.
- The patient can no longer be treated with trial medication for other medical reasons (such as surgery, AEs, other diseases, or pregnancy).
- The patient has repeatedly shown to be non-compliant with important trial procedures and, in the opinion of both the investigator and sponsor representative, is not willing or able to adhere to the trial requirements in the future.

Given the patient's agreement, the patient will undergo the procedures for early treatment discontinuation and follow up as outlined in the [Flow Chart](#) (FC) and [Section 6.2.3](#).

For all patients the reason for withdrawal from trial treatment (e.g. AEs) must be recorded in the CRF. These data will be included in the trial database and reported. Patients who withdraw from treatment prior to disease progression should be encouraged to return for full EOT and follow-up assessments as outlined in the [Flow Chart](#). In particular, a follow-up visit should be performed wherever possible to ensure all adverse events are adequately followed up.

During the MTD evaluation period, patients withdrawn for a reason other than having a DLT or patients who miss more than one visit will be replaced after discussion between the sponsor and the Investigator if the information that needed to be collected during that visit is not available and makes the patient non-evaluatable for the PK analyses or safety parameters (including evaluation for DLTs).

Patients who come off trial due to a DLT will not be replaced.

If a patient should become pregnant during the trial, the treatment with BI 905681 must immediately be stopped. The patient will be followed up until delivery or termination of pregnancy (see [Section 5.2.6.2](#) for information on pregnancy forms). The data of the patient will be collected and reported in the eCRF until the last patient's last visit and any events occurring thereafter will be reported in the BI drug safety database as described in [Section 5.2.6](#).

3.3.4.2 Withdrawal of consent for trial participation

Patients may withdraw their consent for trial participation at any time without the need to justify the decision.

This will however mean that no further information may be collected for the purpose of the trial and negative implications for the scientific value may be the consequence. Furthermore it may mean that further patient follow up on safety cannot occur.

If a patient wants to withdraw consent, the investigator should explain the difference between treatment withdrawal and withdrawal of consent for trial participation and explain the options for continued follow up after withdrawal from trial treatment, please see [Section 3.3.4.1](#) above.

3.3.4.3 Discontinuation of the trial by the sponsor

Boehringer Ingelheim reserves the right to discontinue the trial overall or at a particular trial site at any time for the following reasons:

- Failure to meet expected enrolment goals overall or at a particular trial site
- Emergence of any efficacy/safety information invalidating the earlier positive benefit-risk-assessment that could significantly affect the continuation of the trial
- Violation of GCP, the trial protocol, or the contract impairing the appropriate conduct of the trial
- Completion of treatment by all patients and the sponsor determines that sufficient data have been collected.

The investigator / trial site will be reimbursed for reasonable expenses incurred in case of trial termination (except in case of the third reason).

4. TREATMENTS

4.1 INVESTIGATIONAL TREATMENTS

4.1.1 Identity of the Investigational Medicinal Products

Table 4.1.1: 1 Description of test product BI 905681 solution for infusion:

Substance:	BI 905681
Pharmaceutical formulation:	Solution for infusion Dilution in 0.9% sodium chloride is required
Source:	Boehringer Ingelheim Pharma GmbH & Co. KG
Unit strength:	10 mg/mL (10 mL vial)
Posology	Schedule A; Infusion on Day 1 of each cycle (1 cycle = 21 days) Schedule B; Infusion on Days 1 and 15 of each cycle (1 cycle = 28 days)
Route of administration:	i.v.

4.1.2 Selection of doses in the trial

4.1.2.1 Starting dose for Schedule A

The estimation of the recommended starting dose (RSD) was made on the basis of the ICH Guidance for Industry “S9 Nonclinical Evaluation for Anticancer Pharmaceuticals” ([R11-5034](#)).

Two approaches were taken to calculate the starting dose: (1) use of the HNSTD level determined in the 4-week repeat dose toxicity study in the monkey, the most relevant toxicology species and (2) use of the minimal efficacious dose level determined using an EC₅₀ value from the *in vivo* pharmacology study (Wnt driven breast cancer xenograft model). An approach using the STD₁₀ (a severely toxic dose that causes death or irreversible severe toxicity in 10% of rodents) from the 2-week non-GLP mouse study was not feasible due to morbidity and mortality that was likely a result of anti-drug antibody (ADA) immune complex-related hypersensitivity reactions. The lowest starting dose of 1.0 mg/kg BI 905681 was selected and is expected to be an adequate and safe starting dose.

Approach 1 (use of HNSTD level in the 4-week repeat dose toxicity study in the monkey): The RSD is calculated to be 8.1 mg/kg.

In the 4-week GLP repeat dose toxicity study, the NOAEL was determined to be 150 mg/kg/dose q1w (highest dose tested) and this dose is also considered as the HNSTD based on lack of overt toxicities.

Step 1: Determination of the HNSTD in the repeat dose toxicity study if non-rodent is the most appropriate species (4-week GLP study in the monkey)

Monkey: HNSTD = 150 mg/kg

Step 2: Conversion of 1/6th animal HNSTD to Human Equivalent Dose (HED)

Monkey: 1/6th HNSTD = 25 mg/kg

Conversion factor from monkey dose to HED: 0.324 (based on body surface area scaling factor for the drug molecular weight (43.2 kDa <100 kDa))

HED = 25 mg/kg x 0.324 = 8.1 mg/kg

Approach 2 (use of minimal efficacious dose level determined using an EC₅₀ value from the *in vivo* pharmacology model): The RSD is calculated to be 1.0 mg/kg.

A Wnt driven breast cancer xenograft model has been used as a mechanistic *in vivo* model to test the anti-tumor activity of BI 905681. BI 905681 was administered at doses of 50, 15 or 5 mg/kg by i.v. injection twice per week. The significant tumor regression was achieved at 15 or 50 mg/kg (regression in 7/7 animals) and treatments at these dose levels were well tolerated with no overt clinical signs or significant change in body weight. A dose-dependent pharmacodynamics modulation (inhibition of Axin2 and Notum gene expression) was detected at the end of the efficacy study in tumor tissues. In addition, a PK-PDc time-course experiment performed in the same xenograft model revealed that full pathway modulation (measured by Axin2 down regulation) was achieved up to 48 hours after single dose administration of 15 mg/kg, which corresponded to plasma concentrations higher than 715 nM. Since continuous inhibition of the Wnt pathway is desired, this threshold is considered as the EC₉₀ value of the concentration-effect relationship (in terms of human equivalent C_{trough}). According to the formula [EC_F = (F ÷ (100 - F)) x EC₅₀], and the EC₅₀ of 79.4 nM was calculated which is considered appropriate to determine a starting dose in humans. By simulation of the human PK profile using predicted PK parameters, a human dose of 1.0 mg/kg was estimated to provide a C_{trough} concentration of 77.3 nM at steady state (assuming steady state is reached after 9 weeks), based on a once every three week (q3w) dosing schedule.

The RSD of BI 905681 is 1.0 mg/kg administered via i.v. infusion, which is the lowest starting dose determined by using the EC₅₀ value from the *in vivo* pharmacology model (Approach 2). This dose is expected to be a safe starting dose that has minimal pharmacologic effects and is 8-fold below the RSD determined using the HNSTD from the 4-week repeat dose toxicity study in monkeys.

At the 1.0 mg/kg starting dose, the human exposure is predicted to be C_{max} of 21.8 µg/mL and AUC_{0-168h} of 1,900 µg•h/mL. The steady state combined males and females C_{max} and AUC_{0-168h} at the NOAEL, 150 mg/kg/dose from the 4-week toxicity study in monkeys are 5,290 µg/mL and 498,000 µg•h/mL, respectively. The safety margins are 243X and 262X for

C_{max} and AUC_{0-168h} , respectively. Thus, it is considered that the starting dose of 1.0 mg/kg is a conservative starting dose that should assure the safety of patients in the initial clinical trial, while allowing the potential for benefit. The estimated exposure multiples versus the exposures at the monkey NOAEL are shown in [Table 4.1.2.1:1](#). For further details please refer to the IB.

Table 4.1.2.1:1 Recommended starting dose (1.0 mg/kg) and estimated exposure multiples versus exposures at the monkey NOAEL

C_{max} at the monkey NOAEL (μ g/mL)	Estimated C_{max} at 1.0 mg/kg (μ g/mL)	Exposure Multiple vs Monkey NOAEL $C_{max}^†$	AUC_{0-168h} at the monkey NOAEL (μ g•h/mL)	Estimated AUC_{0-168h} at 1.0 mg/kg (μ g•h/mL)	Exposure Multiple vs Monkey NOAEL $AUC_{0-168h}^†$
5,290	21.8	243X	498,000	1,900	262X

[†]Exposure multiple = C_{max} or AUC_{0-168h} at the NOAEL in monkeys ÷ estimated C_{max} or AUC_{0-168h} at 1.0mg/kg in humans; To calculate the exposure multiples, AUC_{0-168h} at 1.0 mg/kg was estimated from q3w dosing schedule

4.1.3 Dose-escalation scheme

Table 4.1.3: 1 Provisional (Example Only) dose levels for escalation in Schedule A

Dose Level	Proposed dose	Increment from previous dose
1	1.0 mg/kg/q3w	Starting dose
2	2.5 mg/kg/q3w	150%
3	4.5 mg/kg/q3w	80%
4	6.5 mg/kg/q3w	44.4%
5	8.5 mg/kg/q3w	30.8%

At the end of each treatment cohort, BI will convene a meeting with the SMC members. At the dose escalation meeting, the clinical course (safety information including both DLTs and all CTCAE Grade ≥ 2 toxicity data during the DLT evaluation period, and all available PK data) for each patient in the current dose cohort will be described in detail. Updated safety data on other ongoing patients, including data beyond the DLT evaluation period, will be discussed as well. Based on that, a decision on the next dose level to be tested is to be made. Dose escalation will continue until identification of the MTD/OBD, safety concerns arise, or the trial is terminated for other reasons. The absolute maximum clinical dose must not exceed 1120 mg/dose.

4.1.4 Starting Dose for Schedule B

After determination of the MTD/OBD in Schedule A, Schedule B will commence. The starting dose in Schedule B will be determined by the SMC, and will not exceed 30% of the MTD from Schedule A. The SMC will also review whether the planned dosing schedule, assessments and sample collection in Schedule B remain appropriate, and may decide not to

pursue testing of this schedule. Schedule B will utilise its own BLRM and prior distribution will be derived from data in Schedule A.

The dose levels and cohort sizes in Schedule B will be decided by the SMC, following the same process and rules as for Schedule A (described in [Section 3.1](#)). The absolute maximum clinical dose must not exceed 1120 mg/dose.

4.1.5 Method of assigning patients to treatment groups

At any time during the trial, a single dose cohort will be open for recruitment and each patient will be allocated to the next available slot. Medication will be assigned via Interactive Response Technology (IRT) for each treatment cycle. Each medication vial will have a unique medication number.

4.1.6 Drug assignment and administration of doses for each patient

The study drug will be prepared and handled according to the ‘Clinical Supplies Handling Instruction’ which will be filed in the ISF. Upon notification that a patient will be treated in the study, the pharmacy will prepare the study drug at the assigned dosage for administration to the patient.

The Cycle 1 Day 1 dose will be calculated using the Cycle 1 Day 1 weight as the reference weight. If the patient’s weight changes by $\leq 5\%$ compared to the reference weight, the dose (in mg) may remain the same for subsequent cycles. If the weight changes by $>5\%$ the dose will be recalculated and the new weight will be used as the reference weight.

BI 905681 will be given as an i.v. infusion by authorised site staff in a specialised unit where emergency care can be provided (e.g., intensive care unit available, medical personnel trained in advanced life support). The expected infusion time is approximately 60 minutes. Patients must remain under observation for potential signs and symptoms of cytokine release or infusional reactions for at least 6 hours following the end of infusion of BI 905681. If no signs or symptoms are observed during the first three administrations the duration of observation may be reduced to 3 hours for subsequent administrations. For patients who require systemic steroids around the time of administration of BI 905681 or during the post-treatment monitoring period, hospitalisation and monitoring for at least 24 hours is mandatory. Appropriate drugs and medical equipment to treat anaphylactic reactions must be immediately available and study personnel must be trained to recognise and treat anaphylaxis.

No routine premedication will be required for BI 905681 i.v. infusion.

4.1.6.1 Re-treatment criteria

Before administering a treatment dose the investigator must review the assessments performed according to the respective Flow Charts ([Schedule A, Table 10.2:1](#) and [Schedule B, Table 10.2:2](#)) and assess eligibility to receive further treatment and check that the following criteria are met:

- Absence of disease progression
- Drug-related AEs recovered to Grade ≤ 1 (or baseline if higher than Grade 1)
- For AEs that do not require a treatment interruption, a toxicity of CTCAE Grade 2 (e.g. hypophosphatemia, anorexia, neuropathy) may be acceptable, provided the investigator considers it safe for the patient to continue treatment

If the criteria for re-treatment are not met, the patient should be evaluated and the next dose of treatment may be delayed until the criteria are met. For patients on Schedule A the dose may be delayed for up to 14 days. For patients on Schedule B, the dose may be delayed for up to 7 days. Dose reduction may be appropriate and will be discussed in the SMC (see [Section 4.1.6.7](#)).

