Methodology:	
This is a Phase I, open-label, non-randomised study of BI 905681 administered intravenously as a single agent.
 
The trial aims to test two different dosing schedules for BI 905681 (Schedule A: q3w in a 3-week cycle and Schedule B: q2w in a 4-week cycle) with two separate BLRM models; in Schedule A the cycles will be 3 weeks in duration and in Schedule B the cycles will be 4 weeks in duration.

Number of patients entered:	It is anticipated that approximately 60 patients (30 per dosing schedule) will be enrolled in the trial.
Diagnosis :	Patients with advanced, unresectable and/or metastatic solid tumours who are either refractory after standard therapy for the disease or for whom standard therapy is not appropriate.

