- j Pre- and on-treatment tumour biopsy collections for biomarker analyses are mandatory from all patients who have a historically confirmed RNF43 mutation or R-spondin fusion entering the trial from Cohort 2 A total of 2 tumour biopsies are required. The first tumour biopsy may be obtained any time prior to the first dose. For a fresh baseline sample a minimum of 2 core needle biopsies or 1 punch biopsy must be taken

Proprietary confidential information © 2019 Boehringer Ingelheim International GmbH or one or more of its affiliated companies

between Screening and the day before first treatment with BI 905681. An archival sample, from the most recent relapse, will be acceptable as the pre-treatment biopsy, if taken within 6 months of trial start. A second tumour biopsy sample (two core-needle biopsies or 1 punch biopsy, preferably from the same lesion) will be obtained 24 hours after Cycle 2 infusion (the on-treatment biopsy time point may be adapted based on PK analysis). See [Section 5.4.1](#).

- k Bone biomarkers will be assessed on Cycle 1 Day 1, on Cycle 2 Day 1 and then on Day 1 of every odd-numbered cycle and the EOT visit.
- l For detailed schedule, refer to [Appendix 10.2](#).
- m For detailed PK sampling schedule, refer to [Appendix 10.2](#). PK sampling on Day 8 and Day 22 is only required in Cycles 1-4. PK sampling on Day 15 is only required in Cycles 1-6.
- n Blood sample for ADAs is only required on Day 15 of Cycle 1 and Cycle 2. For detailed schedule, refer to [Appendix 10.2](#).
- o Assessment of eligibility for further treatment is required prior to dosing on Day 1 and Day 15 of each cycle from Cycle 1 Day 15 onwards.
- p Patients will be monitored for cytokine release syndrome for 6 hours after the first three administrations of BI 905681 and for 3 hours following subsequent administrations if the previous administrations were well-tolerated.

TABLE OF CONTENTS

TITLE PAGE	1
CLINICAL TRIAL PROTOCOL SYNOPSIS	2
FLOW CHART: BI 905681 (REFMAL 638) SCHEDULE A TRIAL ASSESSMENTS..	7
FLOW CHART: BI 905681 (REFMAL 638) SCHEDULE B TRIAL ASSESSMENTS	10
TABLE OF CONTENTS	13
ABBREVIATIONS	17
1. INTRODUCTION	19
1.1 MEDICAL BACKGROUND	19
1.2 DRUG PROFILE	19
1.2.1 Pharmacology	19
1.2.2 Pharmacokinetics	20
1.2.3 Toxicology	21
1.3 RATIONALE FOR PERFORMING THE TRIAL	22
1.4 BENEFIT - RISK ASSESSMENT	22
2. TRIAL OBJECTIVES AND ENDPOINTS	25
2.1 MAIN OBJECTIVES, PRIMARY AND SECONDARY ENDPOINTS.....	25
2.1.1 Objectives.....	25

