5.2 ASSESSMENT OF SAFETY

The safety of BI 905681 will be assessed by a descriptive analysis of incidence and severity of AEs graded according to CTCAE (Version 5.0), the incidence of DLTs, laboratory data, and results of physical examination. Safety will be assessed in a descriptive way without confirmatory analysis.

Dose-limiting toxicities observed during the MTD evaluation period (first 3 weeks of Schedule A or first 4 weeks of Schedule B) will be considered for MTD determination. However, DLTs observed in all treatment cycles will be considered for determining a recommended Phase 2 dose (RP2D). The BLRM model will be re-run including the DLT information from all cycles. Based on both estimates, the recommended dose for further development will be selected. At regular intervals, all available safety data including AEs qualifying as DLTs will be submitted to the SMC. The SMC will independently assess this information and provide recommendations for trial conduct and dose escalation. If there are too few or no DLTs for BLRM guided dose selection, PK and/or biomarker data will be taken into consideration for RP2D determination.

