6. INVESTIGATIONAL PLAN

6.1 VISIT SCHEDULE

Patients meeting the inclusion and exclusion criteria for the part they are participating in and who have signed a written ICF, are eligible for participation in the trial. Patients will visit the clinical site at the time points specified in [Schedule A Flow Chart](#) and [Schedule B Flow Chart](#) specific to each part. If a patient misses a scheduled visit, and reports to the Investigator between the missed visit and the next scheduled visit, the assessments for the missed visit must be done with the actual date and the reason must be given for the delayed visit. The next visit must then take place at the scheduled time after the first administration of the trial drug in the respective treatment cycle.

Once the decision is made for any reason for a patient to stop the treatment with BI 905681, an EOT visit must occur as soon as possible (no later than 7 days after stopping treatment). After the EOT visit, the patient must undergo a follow-up safety evaluation 42 (+7) days after the last administration of trial therapy.

The trial will be conducted according to the principles of GCP.

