10.3 STATISTICAL APPENDIX INCLUDING MODEL PERFORMANCE AND DATA SCENARIOS

A BLRM with overdose control will be used to guide dose escalation in this study. After patients in each cohort have completed at least one cycle of treatment, the prior distribution will be updated through Gibbs sampling procedures with the accumulated DLT data from the MTD evaluation period (first three weeks of Schedule A and first four weeks of Schedule B). Posterior probabilities for the rate of DLTs will be summarised from BLRM. Selection of the next dose will be based on these probabilities as well as on other safety laboratory and PK data.

The model was assessed by two different metrics: hypothetical on-study data scenarios and long-run operating characteristics.

Hypothetical data scenarios

Hypothetical data scenarios for dosing Schedule A are shown in [Table 10.3:1](#). These scenarios reflect potential on-study data constellations and related escalation as allowed by the model. For each scenario, the probability of overdose for the current dose, as well as the next potential dose and related probabilities of under-dosing, target dose and over-dosing are shown. The actual dose chosen for the next cohort, not shown in the [Table 10.3:1](#), will be determined by the SMC after taking into consideration the recommended dose from the model as well as other relevant data from this study.

For example, scenario 1 corresponds to the case where no DLT is observed at the first two dose levels, then the next permitted dose is 4.5 mg/kg/q3w.

In scenarios 2 to 6, it is assumed that no DLT is observed until the dose level of 4.5 mg/kg/q3w. Scenarios 3 to 6 focus on the case where the dose level of 6.5 mg/kg/q3w is identified as the MTD. To be more specific, in scenario 3, when 1 DLT is observed at 4.5 mg/kg/q3w, the next dose permitted by the model is the same dose level and we enroll 3 more patients at 4.5 mg/kg/q3w in scenario 4 and observed no DLT. In this case, the model advises to escalate to the next dose level of 6.5 mg/kg/q3w. Assuming 1 DLT is then observed at 6.5 mg/kg/q3w, which is demonstrated in scenario 5, the model proposed to stay at dose level of 6.5 mg/kg/q3w and enroll 3 more patients. Finally in scenario 6, assuming 1 additional DLT is observed, the criteria for MTD are met and 6.5 mg/kg/q3w is claimed to be the MTD.

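### In Schedule B the Cycle 1 Day 15 infusion may be delayed by up to 7 days but the DLT window stays at four weeks, so follow-up after the second infusion can fall from 14 to 7 days in a patient the BLRM counts as fully observed

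*Protocol*

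**What the plan says.** **Dosing.** Protocol Section 4.1.1 sets the regimen: "Schedule B; Infusion on Days 1 and 15 of each cycle (1 cycle = 28 days". The synopsis describes it as "Schedule B: q2w in a 4-week cycle".

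**Delay.** Section 4.1.6.1 applies before any treatment dose, not only before a new cycle, and states: "For patients on Schedule B, the dose may be delayed for up to 7 days". Footnote o of the Schedule B flow chart makes the eligibility check "required prior to dosing on Day 1 and Day 15 of each cycle from Cycle 1 Day 15 onwards". The second infusion of Cycle 1 is therefore covered.

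**DLT window.** Section 2.1.2 ties the MTD to the first cycle and equates this with 4 weeks in Schedule B. Section 5.2 gives the window as "first 3 weeks of Schedule A or first 4 weeks of Schedule B", and Section 10.3 feeds the BLRM with DLTs from the "first three weeks of Schedule A and first four weeks of Schedule B". Section 7.3.1 agrees. None of them extends the window when the Day 15 dose is late.

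**Who counts.** Section 3.3.4.1 provides for replacing patients who withdraw without a DLT or miss more than one visit. A delayed dose is not listed. The delay-based DLT criterion in Section 4.1.7 concerns only a late start of Cycle 2.

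**Start of Cycle 2.** No section says when it falls after a delayed Day 15 infusion. Section 6.1 says of missed visits: "The next visit must then take place at the scheduled time after the first administration of the trial drug in the respective treatment cycle". Section 6.2 allows for delayed cycles, but only when timing tumour assessments.

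**The concern.** The delay rule moves the second infusion and the DLT window does not move with it. A patient held at Day 15, typically for unresolved drug-related toxicity, is then watched for a shorter time after the second infusion than a patient dosed on schedule. Both enter the escalation model as one complete observation.

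DLTs that start after Day 28 are left out of the model that sets the next dose and the MTD. The error runs in one direction: the Schedule B DLT rate is understated and the MTD tends to be too high. That works against the overdose control on which the design relies.

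A second gap follows. Because the start of Cycle 2 is undefined in this situation, neither the interval to the third infusion nor the length of the first cycle is settled.

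Schedule A does not share the problem. It has one infusion per cycle, so a delayed dose is Cycle 2 Day 1 or later, after the 21-day window has closed.

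**Working it through.** **Inputs from the Protocol.** Infusions on Days 1 and 15 and a 28-day cycle (4.1.1); delay of up to 7 days (4.1.6.1); window of 4 weeks, Days 1 to 28 (5.2, 7.3.1, 10.3); Day 1 visit window of ±72 h (Schedule B flow chart); overdose range from 0.33 upwards (7.1).

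**Step 1: the plan's own timing.**
- Infusion 1 to infusion 2: 15 − 1 = 14 days.
- Infusion 2 to Cycle 2 Day 1: 29 − 15 = 14 days.
- DLT follow-up from infusion 2: 28 − 15 + 1 = 14 days.
- Table 10.2:2 agrees: 336 h is Day 15 and 504 h is Day 22.

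**Step 2: with a delay of d days.** Infusion 2 falls on Day 15 + d. Follow-up within the window is 28 − (15 + d) + 1 = 14 − d days.

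| Delay (days) | Infusion 2 | DLT follow-up (days) |
|---|---|---|
| 0 | Day 15 | 14 |
| 3 | Day 18 | 11 |
| 5 | Day 20 | 9 |
| 7 | Day 22 | 7 |

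**Step 3: start of Cycle 2 after a 7-day delay.** Two readings are open.
- *28-day cycle unchanged.* Cycle 2 Day 1 is Day 29, so the third infusion follows 29 − 22 = 7 days after the second (4 to 10 days with the ±72 h window).
- *Cycle stretched to keep 14 days.* The third infusion is on Day 22 + 14 = Day 36 and Cycle 1 lasts 35 days. The first cycle and the first 4 weeks are then different DLT windows. The four-week window still gives only 7 days after infusion 2.

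**Step 4: effect on the DLT rate.** The documents give no onset distribution or per-infusion risk. Assume equal, independent risk q per infusion and onset uniform over the 14 days after it. Let s be the fraction delayed by the full 7 days among patients without a DLT from infusion 1.
- True first-cycle rate: 1 − (1 − q)².
- Observed rate in a fully delayed patient: 1 − (1 − q)(1 − q/2).
- Loss per fully delayed patient: (1 − q) × q/2.

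At q = 0.20 the true rate is 1 − 0.80² = 36%. The rate observed in a fully delayed patient is 1 − 0.80 × 0.90 = 28%, a loss of 8 percentage points. Overall, the observed rate is 36% − 8s percentage points:

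| Fraction delayed s | Observed rate |
|---|---|
| 0.10 | 35.2% |
| 0.20 | 34.4% |
| 0.375 | 33.0% |
| 1.00 | 28.0% |

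At q = 0.15 the true rate is 1 − 0.85² = 27.8% and the rate in fully delayed patients is 1 − 0.85 × 0.925 = 21.4%. Both lie in the target range.

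**The case against.** **Later DLTs are not ignored.** Section 4.1.7 takes later-cycle DLTs into account where available, and it considers time to onset and dosing delays when deciding what counts as a DLT for escalation. Under Section 4.1.3 the SMC discusses data from beyond the DLT period. Sections 5.2 and 7.3.1 re-run the BLRM with DLTs from the whole treatment period before a dose is recommended. Re-treatment criteria are checked again before Cycle 2. This stands as partial mitigation. Most of it is discretionary or comes later, and the model used for escalation and MTD determination still takes the fixed window.

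**Few patients may be affected.** Anyone with a DLT after infusion 1 is already counted. The loss arises only when a non-DLT problem blocks Day 15 and clears within a week, and Section 4.1.6.1 allows dosing to go ahead with some Grade 2 toxicities. Reactions soon after an infusion would be seen within 7 days in any case. This also stands, and it is why the size must be stated as a function of s.

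**A one-week infusion gap is not prescribed.** A reader might infer from Section 6.1 that Cycle 2 Day 1 must stay on Day 29, so that the plan contradicts its own two-weekly schedule. The documents do not support that. The Section 6.1 sentence deals with missed visits, not doses held for toxicity, and Section 6.2 recognises delayed cycles. The short interval is permitted by silence; it is not a stated rule.

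**Schedule B was provisional.** Under Sections 3.1 and 4.1.4 the SMC was to review the schedule and its assessments before opening it. That was an opportunity to repair the text, but it does not put the missing rule into the text.

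**Conclusion.** The gap in the DLT window is real and follows from stated rules. Follow-up after the second infusion shrinks by one day per day of delay, to 7 of 14 days at the permitted maximum, while the patient remains evaluable and counts as fully observed. The start of Cycle 2 after such a delay is undefined, and neither reading restores follow-up under a four-week window.

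The direction of bias is towards too high a Schedule B MTD. Its size is unknown and probably modest. On the assumptions above (20% per infusion, independence, uniform onset, full 7-day delays) the observed rate is 35.2% with 10% of patients delayed and 34.4% with 20%, both still in the overdose range. It drops below 33% only if more than 37.5% are delayed. A reader might take the contrast of 36% with 28% as the expected error, but it requires every patient to be delayed by the full week. Shorter delays or earlier onset would reduce the loss; higher second-infusion risk in delayed patients would increase it.

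No reported result is affected. SAP Section 4 records that only Schedule A was investigated, and SAP Section 6.1 that the trial ended before Schedule B began. The point concerns the Protocol's design and any reuse of its text.

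**What to change.** In Protocol Sections 2.1.2, 5.2, 7.3.1 and 10.3, define the Schedule B MTD evaluation period as ending at the later of 28 days from the first infusion or 14 days after the second Cycle 1 infusion. Run the BLRM only once each patient has reached that point, and count DLTs starting within it.

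Sections 4.1.1, 4.1.6.1, 4.1.7, 6.1 and 6.2 must be reconciled on when Cycle 2 starts after a delayed Day 15 infusion. The revised window depends on this. After a Day 22 infusion it would cover Days 22 to 35. If Cycle 2 began on Day 29, a third infusion would fall inside it and the model would mix two-infusion and three-infusion exposure. The clinical rule is for the sponsor to decide.

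The cost is protocol wording and up to about one extra week (Day 35 rather than Day 28) before a cohort decision when a patient has been delayed. No extra patients are needed.
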